## **STATISTICAL ANALYSIS PLAN**

For the purpose of testing the null hypothesis that shows equal live birth rates in the group of women who undergo elective deferred transfer of a single embryo and the group that undergoes elective transfer of a fresh embryo, a power of 80% has been established to detect statistically significant differences using a bilateral Chi-square test for two samples, taking into account that the significance level is 5%, and assuming that the proportion in the group of women undergoing a fresh transfer is 50.9%, the proportion in the group of women undergoing elective deferred transfer is 78%, and that the proportion of women out of the total is 50%, it will be necessary to include 48 women in each group, for a total of 96 experimental units in the study.

Taking into account that the expected dropout rate is three out of ten women, it will be necessary to include 69 women per group.

The assignment of the 138 women to one of the groups will be carried out by a randomized procedure, following a sequence of random numbers generated by specific software (Epidat, Epidemiological Analysis of Tabulated Data Program. Tabulated. Version 3.1)

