## **STUDY PROTOCOL:**

The study was designed as a prospective, randomized, two-arm, parallel, unblinded study, during which We will include 138 couples (69 in each group) of IVF / ICSI users. Cycles canceled or without transfer (either due to not obtaining oocytes, non-fertilization or arrest of embryonic development) will not be included in the study. The assignment of the pairs to each of the groups will be carried out by means of a random sampling procedure. The randomization list will be created specifically for this project and will be guarded by an outsider to the research team:

- Group I (experimental): fresh transfer is not performed, the best quality embryo is cryopreserved. Elective transfer in a later cycle of the cryopreserved embryo.
- Group II (control): fresh transfer of the best quality embryo.

Couples will be able to participate in the study for only one cycle. Each couple will be interviewed by a member of the team who will explain the characteristics of the study and they will be given an Information Sheet. It is necessary to obtain the written informed consent of each couple. The person outside the investigation team who is guarding the randomization list will assign the corresponding treatment group.

Before starting the study, ethical approval will be processed by the Ethics Committee through the Ethics Portal of the Biomedical Research of Andalusia.

Patients must follow ovulation stimulating treatment, in order to achieve multiple follicular development. A "long analog" GnRH agonist protocol will be used. This consists of administering from the day 22 of the cycle 0.1 mg / day of GnRH analog (Decapeptyl 0.1; Lasa, Barcelona, Spain) until the day the gonadotropin administration, in which the dose is reduced to 50% until the day of hCG. After 10-14 days of administration of the agonist, we proceed to check the pituitary braking by means of ovarian vaginal ultrasound (absence of follicles and cysts). Then, 300 IU of recombinant FSH (rFSH) is administered per day (Gonal F, Merck, Madrid, Spain) for two days, and 150 IU of FSHr from the 3rd to the 7th day. On this day, ultrasound control of the follicular development is accomplished in order to re-adjust the dose of rFSH to each patient. Once the follicular response is adequate (more than 3 ovarian follicles greater than 18 mm in diameter), we proceed to trigger ovulation using 6500 IU hCG (Ovitrelle, Merck, Darmstadt, Germany).

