The embryo transfer will be carried out in group 2 on the third day, choosing the best embryo according to the previous criteria. In Group 1 embryos will be cryopreserved by vitrification, selecting the best one for deferred transfer. The commercial vitrification media will be Medicult Vitrification, and the storage device will be Cryoleaf (McGill Cryoleaf, Medicult, Denmark). All cryopreserved embryos will be stored in liquid nitrogen at -196°C in storage cylinders (Air Liquide, France). The day before cryotransfer, the embryo is devitrified, using the thawing kit (Medicult Warming, Denmark). At the end, the embryos are washed in G2 medium (Vitrolife), leaving them in cultivation until the following day, after evaluation of embryonic quality and cryosurvival (percentage of lysed cells). The endometrium of the woman is prepared by treatment with estradiol valerate and progesterone. The day of the cryotransfer embryonic quality is assessed again, emphasizing embryonic division. Cryotransfer is done by the same technique than fresh transfer.

Workplan:

First year:

- Our center is routinely able to carry out the vitrification, so it is not necessary to fine-tune our techniques.
- Design of the Access database with the variables to be analyzed.
- Beginning of the interviews and selection of patients
- Beginning of the IVF/ICSI cycles and cryotransfers.

Second year:

- Continue with the selection of patients until completing the expected number.
- Continuation of IVF/ICSI cycles and cryotransfer.
- Carry out an intermediate analysis of the data using "adaptive clinical designs".

Third year:

- Continuation of IVF/ICSI and cryotransfer cycles.
- Collection of data from IVF/ICSI and neonatal cycles and application of statistical treatment.
- Drafting of results

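### Does the SAP need an effect estimate with a confidence interval, and a statement on adjustment, beyond the chi-square in its sample-size sentence?

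*Combined protocol and SAP*

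**What the plan says.** The Statistical Analysis Plan has three short paragraphs: the sample size, the allowance for dropout, and the random-number software. The first opens with the purpose of "testing the null hypothesis that shows equal live birth rates" in the deferred-transfer and fresh-transfer groups. It then sets 80% power "to detect statistically significant differences using a bilateral Chi-square test for two samples" at the 5% level, with assumed rates of 50.9% (fresh) and 78% (deferred), and ends with "it will be necessary to include 48 women in each group, for a total of 96 experimental units in the study". Dropout of three in ten raises this to 69 per group.

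The Workplan in the Study Protocol section adds little about the final analysis. The first year includes "Design of the Access database with the variables to be analyzed", without listing the variables. The third year includes "Collection of data from IVF/ICSI and neonatal cycles and application of statistical treatment", without naming a method.

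No section names a risk difference, risk ratio, odds ratio or confidence interval. None mentions a covariate or a regression model, or states that the analysis will be unadjusted.

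**The concern.** Two things seem to be left open.

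**Precision.** The trial is sized for a large effect. If the true effect is smaller, the likely result is a non-significant p-value that could mean either little benefit or too few women to tell. Only an estimate with an interval separates the two, and the plan does not commit to one.

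**Choice of analysis.** The design section says "The study was designed as a prospective, randomized, two-arm, parallel, unblinded study", and the variables are not listed. If an adjusted result were published, a reader could not check from this plan whether the crude or the adjusted comparison had been chosen after the outcomes were seen. Such a choice inflates the type I error.

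**Working it through.** **1. The plan's own figures.** Inputs from the Statistical Analysis Plan: p1 = 0.509, p2 = 0.78, two-sided 5%, power 80%, equal groups. The mean rate is (0.509 + 0.78)/2 = 0.6445. With the pooled-variance formula and no continuity correction,

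n = [1.960 × √(2 × 0.6445 × 0.3555) + 0.842 × √(0.509 × 0.491 + 0.78 × 0.22)]² / 0.271²

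= [1.960 × 0.6769 + 0.842 × 0.6492]² / 0.0734 = 3.509 / 0.0734 = 47.8, so 48 per group.

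With dropout, 48 / (1 − 0.3) = 68.6, so 69 per group. Both stated figures reproduce. They match the uncorrected, unadjusted two-sided chi-square; the continuity-corrected version would need 55. The sample size is therefore consistent with a crude 2×2 comparison as the intended test.

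**2. How much a p-value alone would hide.** Uncorrected chi-square and Newcombe 95% interval at 48 per group, with 24/48 births after fresh transfer (illustrative counts):

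| Deferred | Difference (points) | p | 95% interval (points) |
|---|---|---|---|
| 33/48 | 18.8 | 0.061 | −0.8 to 36.4 |
| 34/48 | 20.8 | 0.037 | 1.3 to 38.3 |

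One birth changes the verdict while the interval hardly moves, and both intervals contain the planned 27.1 points.

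Exact enumeration over all possible pairs of counts, with a fresh rate of 50.9%:

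| Deferred rate | Analysed per group | Power | Mean interval half-width (points) | Non-significant results whose interval contains 27.1 |
|---|---|---|---|---|
| 78% (planned) | 48 | 80.6% | 17.7 | 84% |
| 64.45% (half effect, assumed) | 48 | 27.0% | 18.7 | 53.9% |
| 64.45% (half effect, assumed) | 69 | 35.8% | 15.8 | 37.7% |

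The half effect is 27.1/2 = 13.55 points, and 50.9 + 13.55 = 64.45%. The imprecision is real, and it is a property of the sample size. Writing an interval into the SAP would display it, not reduce it.

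**3. Would an interval change the decision?** In the same enumeration at 48 per group and the planned rates, the Newcombe interval and the chi-square disagree about significance with probability of about one in a million. The interval adds information and leaves the conclusion of the test as it was. It also needs no input beyond the births and denominators in each group.

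**4. What a free choice between crude and adjusted tests could cost.** From 200,000 simulated null trials with 48 per group and one balanced binary factor, the type I error when either the crude or the Mantel-Haenszel test may be claimed is 5.4%, 5.9%, 6.3% and 6.8% for factor odds ratios of 1, 2, 3 and 5. The crude test alone gives 5.1% to 5.2%. The odds ratios and the split are assumptions; the documents name no factor at all. For odds ratios of 1 to 2 the excess is less than one percentage point.

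**The case for a change.** The best case for a change is that the text really is silent and the remedy is cheap. Inferring the chi-square as the primary test settles neither the effect scale and interval nor whether adjustment is allowed. Authors may well report an interval unprompted, but nothing binds them to do so. A few sentences would settle all of this without touching the test, the sample size or the conduct of the trial, and in an open-label trial a reader would be glad of them.

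The silence stands, and so does the value of an interval here. What does not stand is the step from silence to defect. Nothing says that only a p-value will be reported; that scenario is supplied by the concern. Adjustment is a risk only if analysts introduce covariates that the plan never mentions, and the larger inflation figures need strong prognostic factors (odds ratios of 3 to 5) assumed from outside the documents. The open-label design adds little to the argument, because a choice between crude and adjusted results can also be made once a blinded trial has been unblinded.

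**Conclusion.** The observation about the text is correct, but no change to the plan is required. The opening sentence of the Statistical Analysis Plan states the hypothesis, outcome, groups, test, sidedness and level, which is enough to carry out an unadjusted primary analysis. Followed as written, for a single final comparison, it gives a valid test with type I error of 5.1% to 5.2% at 48 per group, and the planned numbers are arithmetically sound. The missing effect measure and interval are details that a competent analyst supplies as a matter of course, and they can be calculated from the group counts. With no covariate named, the default is no adjustment.

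The practical size is modest. At an assumed half-size effect, an interval would show that 54% of non-significant results (48 per group), or 38% (69 per group), had not excluded the planned 27.1 points. That is useful to a reader but does not alter the test. The sponsor may wish to state that the primary comparison is unadjusted, that the rates and risk difference will carry a 95% interval, and that any adjusted analysis is secondary with covariates fixed in advance. This is a reporting courtesy, not a correction.

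The conclusion covers only the form of the final live-birth comparison. The exclusion of cycles without transfer and the second-year interim analysis raise separate questions and are not judged here.

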Oocyte retrieval will be performed by transvaginal ultrasound-guided follicular puncture 36 hours after the injection of hCG, anticipating the ovulatory process, using an ovarian puncture needle (Labotect LaborTechnik-Göttingen, Göttingen, Germany). The follicles larger than 17 mm are punctured one by one, aspirating their content into fluid collection tubes.

The content of the aspirated follicle should be transported quickly to the laboratory to immediately check for the presence of the cumulus-oocyte complex. Antibiotic prophylaxis is not routinely performed, and only in cases where the puncture is more difficult, a single dose of 1,500 mg of cefuroxime sodium will be administered intravenously (Cefuroxime Normon EGF, Madrid, Spain) or 1000 mg of erythromycin lactobionate (Pantomycin Abbot, Madrid, Spain) in patients allergic to beta-lactams. Once the follicular fluid (FF) arrive at the laboratory, the search and identification of the cumulus-oocyte complexes is performed by locating them under stereomicroscopic vision in a 100x15 mm Petri. They are placed in a new 35x10 mm Petri dish inside a few drops of MOPS culture medium Vitrolife (IVF Science Scandinavia, Gothenburg, Sweden) previously aerated and heated to 37°C, to eliminate the remains of FF.

IVF/ICSI and embryo culture will then be performed. To perform sperm microinsemination (ICSI) it is necessary to remove the cumulus and corona radiata from the oocyte. To decumulate, the crown-oocyte cluster complex is submerged in a solution with 80 IU / mL hyaluronidase (HYASE, IVF Science Scandinavia, Gothenburg, Sweden) for 10-20 seconds aspirating the complex several times using a pasteur pipette. The microinsemination technique is performed under a microscope inverted with Eppendorf and Narishigue micromanipulators and microinjectors. In Vitro Fertilization (IVF) is performed in a five-well plate, depositing 0.5 mL of IVF medium (Vitrolife, Sweden) and 0.5 mL of Ovoil (Vitrolife, Sweden) in each well. Five clusters are left per well and 100,000 sperm/mL are added.

In both cases, the oocytes are cultured in a Thermo-Fisher incubator, within a morphokinetic platform (PrimoVision). The following days are evaluated for their classification, choosing the one of better implantation potential according to the division times measured by morphokinetics and the morphological criteria of the Spanish Association for the Study of Reproduction Biology (ASEBIR) reviewed in 2015.

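### Should the live-birth comparison be adjusted for embryo grade rather than rest on a crude chi-square?

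*Combined protocol and SAP*

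**What the plan says.** The SAP names one test for live birth, and does so inside its sample-size sentence: "a power of 80% has been established" "to detect statistically significant differences using a bilateral Chi-square test for two samples". It gives no covariate, regression model or stratified analysis, and no stratified randomisation is described.

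In the STUDY PROTOCOL section, the laboratory classifies embryos by "choosing the one of better implantation potential according to the division times measured by morphokinetics and the morphological criteria". For the control arm, "The embryo transfer will be carried out in group 2 on the third day, choosing the best embryo according to the previous criteria". For the experimental arm, "In Group 1 embryos will be cryopreserved by vitrification, selecting the best one for deferred transfer". The deferred arm is assessed again after warming and on the day of cryotransfer; the fresh arm has no counterpart to this. The trial is described as a "prospective, randomized, two-arm, parallel, unblinded study". The first-year workplan includes "Design of the Access database with the variables to be analyzed", but the variables are not listed.

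**The concern.** The protocol ranks embryos by implantation potential, so it treats grade as informative about a step on the way to live birth. The assessment is made in both arms, yet the analysis does not use it. Adjusting a binary outcome for a prognostic baseline variable, and reporting a standardised risk difference, generally narrows the confidence interval at no cost in patients. The design has almost no slack over its 80% target. A chance imbalance in embryo quality between two arms of 48 would also be easier to handle with an adjustment fixed in advance than with one added afterwards. At stake would be some power and a somewhat wider interval than necessary.

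**Working it through.** **Inputs from the SAP.** Live-birth rates p1 = 0.509 (fresh) and p2 = 0.78 (deferred); two-sided 5% level; 80% power; equal allocation; 48 evaluable per arm; 30% dropout; 69 enrolled per arm.

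**1. The plan's own figure.** The mean rate is (0.509 + 0.78)/2 = 0.6445 and the difference is 0.271. The uncorrected chi-square formula is

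n = [1.96·√(2·0.6445·0.3555) + 0.8416·√(0.509·0.491 + 0.78·0.22)]² / 0.271² = 47.8, so 48 per arm.

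Dropout: 48/0.7 = 68.6, so 69 per arm. Both stated figures reproduce.

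**2. Crude power and precision at 48 per arm.**
- Null SE: SE0 = √(2·0.6445·0.3555/48) = 0.0977.
- Alternative SE: SE1 = √[(0.509·0.491 + 0.78·0.22)/48] = 0.0937.
- Power = Φ[(0.271 − 1.96·0.0977)/0.0937] = 80.2%.
- 95% CI half-width = 1.96·0.0937 = 18.4 points.

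**3. Gross gain from adjustment.** If grade explains a share R² of outcome variance, both SEs are multiplied by √(1 − R²). The documents give no R², so these values are assumptions.

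| Assumed R² | Power | Half-width |
|---|---|---|
| 0 | 80.2% | 18.4 |
| 0.02 | 81.0% | 18.2 |
| 0.05 | 82.2% | 17.9 |
| 0.10 | 84.2% | 17.4 |

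**4. A plausible R².** For a two-level grade with share s in the top level and live-birth gap g, R² = g²·s(1 − s)/0.2108, where 0.2108 is the mean of the two arms' p(1 − p). With an assumed g of 0.20:
- s = 0.5: 0.04·0.25/0.2108 = 0.047.
- s = 0.8: 0.04·0.16/0.2108 = 0.030.
- s = 0.9: 0.04·0.09/0.2108 = 0.017.

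Both arms transfer the best embryo available, which tends to narrow the range of grades and favours the lower values.

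**5. Net of the parameters estimated.** One extra parameter inflates the variance by about 1 + 1/92 = 1.011. A four-level grade (an assumption; the documents do not give the number of levels) needs three parameters, for about 1 + 3/92 = 1.033.

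| Assumed R² | Gross power | Net, two levels | Net, four levels |
|---|---|---|---|
| 0 | 80.2% | 79.8% | not shown |
| 0.017 | 80.9% | 80.4% | 79.6% |
| 0.030 | 81.4% | 81.0% | 80.1% |
| 0.047 | 82.1% | 81.7% | 80.8% |
| 0.10 | 84.2% | 83.9% | not shown |

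From unrounded values, the two-level change for R² of 0.017 to 0.047 is +0.3 to +1.5 points. The four-level change is −0.6 to +0.6.

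**6. Simulation.** With 6,000 trials per case and a standardised logistic estimate, crude versus adjusted power was 80.0% versus 81.2% (20-point gap, 80/20 split) and 80.0% versus 82.0% (20-point gap, 50/50 split). With no gap it was 80.8% versus 80.5%. The Monte Carlo error is about 0.5 points. The two 20-point-gap gains are slightly above the net formula but of the same order. In the two null settings simulated, type I error was the same for both methods (5.5% and 4.8%, Monte Carlo error 0.3).

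**7. Scale.** R² = 0.05 is worth 48/0.95 = 50.5 women per arm, or about 2.5 more. If 51 rather than 48 of the 69 enrolled in each arm were evaluable, crude power would be 82.6%.

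**8. Is the grade a safe covariate?** The documents do not establish any of the conditions:
- The day of grading is given for the fresh arm only.
- Whether the grade is entered in the database is unknown.
- Randomisation is not timed relative to grading. The protocol describes interview, consent and assignment ahead of its account of stimulation, which suggests that assignment comes first without saying so.
- Staff are not blinded, so the grader may know the arm.

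**The case for a change.** The best case for a change is that it is cheap and can be made safe. Only the grade at selection would be used, before transfer or vitrification and never after warming. At that point the arms have not yet diverged in treatment, so a grade assigned without knowledge of the arm would behave like a baseline value. The loss if grade is uninformative is about 0.4 points. If R² reached 0.10, the net gain would be about 3.7 points, or equivalently 44 rather than 48 evaluable women per arm would suffice. A prespecified adjustment also answers any later question about chance imbalance.

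Much of this stands. The method is sound and the arithmetic is right. What does not stand is the claim of low cost. Making the covariate safe requires arm-blind grading, a common grading time in both arms and a fixed point of randomisation. Those are changes to laboratory practice, not only an added database field. Without them the sensible course is to keep the crude comparison as primary, which is the test the SAP already names. Selection also uses division times as well as morphology, so the number of levels and any collapsing rule would have to be settled. At the design rates only about 11 women in the deferred arm (48 × 0.22 = 10.6) would have no live birth, which leaves little room for a finely divided grade.

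**Conclusion.** No change is needed. The chi-square is valid, the sample size reproduces exactly, and planned power is met at 80.2%. Adjusting for a two-level embryo grade would change power by about −0.4 points if grade predicts nothing, by +0.3 to +1.5 points for R² of 0.017 to 0.047, and by about +3.7 points at R² of 0.10. With four levels the benefit over the first range largely disappears. All these figures rest on assumed R² values, because the documents give no prognostic strength for grade and no distribution of grades among selected embryos.

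That is a fair trade-off to decline. A small and uncertain gain in precision does not justify resting the primary result of an unblinded trial on a measurement that may follow assignment and may be made with the arm known. An analyst who finds the grade recorded in both arms before transfer or vitrification can add an adjusted risk difference as a sensitivity analysis without altering the plan's primary comparison. The timing of randomisation and the handling of couples without a grade are missing details, and they matter here only if such an adjustment is made.
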